2.2.1 IMPROVE trial organizational chart

3.0 Study overview

We will conduct a randomized, double blind, placebo-controlled, feasibility study of mometasone furoate, an inhaled cortico-steroid (ICS), for 16 weeks in individuals with SCD and recurrent cough or wheezing who do not meet clinical criteria (derived specifically for individuals with SCD) for a diagnosis of asthma. Participants will be enrolled when they are pain free and have no acute respiratory symptoms. The sample size will be 45 participants, aged ≥ 15 , with 2:1 allocation of drug to placebo. Feasibility will be determined by the proportion of individuals successfully randomized who maintain good adherence and complete at least 30 pain diaries vs. the total number enrolled.

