4.3 Study medication

As already approved by the ISMMS research pharmacy, study medication will be stored in [name] office in a locked cabinet. Thermostat will be set at all times to maintain acceptable storage temperature (59-86 °F). Throughout the week, temperature and humidity (current readings as well as min and max for both) will be logged daily on the study medication temperature log sheet (CRF13) using a Fisher Scientific digital Traceable Thermometer/Clock/Humidity monitor. Over the weekend, min and max temperature and humidity will be logged on the Monday following. Min and max temperatures are stored after the memory is cleared (once each day). [name] packages, dispenses, and maintains accountability for all study medication is assisted by the unblinded RC in packaging and distribution.

Study packets for randomization will be made from sealable envelopes. Each packet will contain sufficient medication for 8 weeks (one 60-dose mometasone twisthaler or one placebo metered dose inhaler MDI). Packets containing active medication will include 'protocol orientation module A' (a document that has training and usage instructions for the mometasone twisthaler). Packets containing placebo will contain 'protocol orientation module B' (a document that has training and usage instructions for the placebo inhaler). Each packet will also include 60 pain diaries. Packets will then be sealed and labeled with a code. The code will indicate which treatment arm the packet corresponds to. The unblinded RC will have access to a master list that reveals the coding scheme, SRC and PI will not have access to this list.

In the event that [name] is not present during study recruitment/enrollment, licensed nurse practitioner [name] will be present to oversee dispensation of study drug or placebo.

5.1 Recruitment, screening and eligibility procedures:

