5.3.4 Randomization and Enrollment

5.3.4.1 Overview

Individuals who meet inclusion/exclusion criteria will then be consented and randomized. The enrollment procedure is designed to maintain blinding of the participant, the PI and the senior RC. One RC will be unblinded (RC2) for purposes of introducing the study medication, training in proper use of the medication and refilling medication if the participant loses their medication.

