Let's take a few minutes to review inhaler use and make sure each of you is using the best technique.

How To Use YOUR INHALER

HOW TO USE ASMANEX TWISTHALER OR GIVE TO YOUR CHILD

- Remove the ASMANEX TWISTHALER from its foil pouch and write the date on the cap label.
- Throw away the inhaler 45 days after this date or when the dose counter reads “00”, indicating the final dose has been inhaled, whichever comes first.
- Follow steps 1 and 2 below each time you inhale a dose from your ASMANEX TWISTHALER.

Inhaler Parts:

[figure not shown]
See Figures 1 and 2 below to become familiar with the inhaler parts.

Step 1: Open inhaler

Hold the inhaler straight up (upright position) with the colored portion (the base) on the bottom (see Figure 3 below). It is important that you remove the cap of the TWISTHALER while it is in this upright position to make sure that you get the right amount of medicine with each dose.

Holding the colored base, twist the cap in a counterclockwise direction to remove it (see Figure 3 below). As you lift off the cap, the dose counter on the base will count down by one. Removing the cap loads the TWISTHALER with the medicine that you are now ready to inhale.

IT IS IMPORTANT TO NOTE that the indented arrow (located on the white portion of the TWISTHALER, directly above the colored base) is pointing to the dose counter (see Figure 2).

Step 2: Inhale dose

Breathe out fully. Then bring the TWISTHALER up to your mouth or your child's mouth with the mouthpiece facing toward you or your child. Place the mouthpiece in your mouth or your child's mouth, holding it in a horizontal (on its side) position as shown below (see *Figure 4*). Firmly close your lips around the mouthpiece and take in a fast, deep breath. Since the medicine is a very fine powder, you may not be able to taste, smell, or feel it after inhalation. Do not cover the ventilation holes while inhaling the dose.

[figure not shown]

Figure 4: Inhalation

Remove the TWISTHALER from your mouth and hold your breath for about 10 seconds, or as long as you comfortably can.

IMPORTANT: DO NOT BREATHE OUT (EXHALE) INTO THE INHALER.

After you take your medicine, it is important that you wipe the mouthpiece dry, if needed, and then **REPLACE THE CAP**, firmly closing the TWISTHALER right away (see *Figures 5 and 6* below).

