As part of this study you will be given an inhaler. This inhaler may contain placebo (no medication) or it may contain a medicine called mometasone. Mometasone is part of a class of medications called corticosteroids.

This is a medication taken regularly every day even when you don't have any symptoms

Although they have a similar name, these steroids are very different from the anabolic steroids that have been in the news in recent years because of their ill-advised use by athletes to increase muscle mass.

Corticosteroids are:

- Anti-inflammatory-Corticosteroids are a very effective anti-inflammatory medication and help reduce or prevent edema and excess mucus in the bronchial tubes.
- Have delayed action-· Corticosteroids do not relax the muscles around the bronchial tubes and will not open the airways immediately as do the bronchodilators. For this reason, they may not *seem* to have any effects. However, over time they can be very beneficial in reducing inflammation.

Inhaled corticosteroids have very few side effects, when used in moderate doses, but they must be taken regularly to be effective.

Possible side effects: an unpleasant taste and gastrointestinal symptoms (e.g., nausea). They may cause a yeast infection ("thrush") in the mouth or bother the upper airways and cause coughing.

Proper Inhaler Use (10 minutes)

The medication that we have been discussing is administered by aerosol inhaler, and proper inhaler use is very important for maximum benefit. If inhalers are not used correctly, the medications don't help much because they can't get all the way down into the narrow airways. Many times patients stop using their inhalers (or, on the other hand, overuse their inhalers) because they think the medicine is not working. In reality, it's not working only because they aren't using it right.

Go over steps while you demonstrate correct usage.

Instruct participants to take one puff per day

Let's take a few minutes to review inhaler use and make sure each of you is using the best technique.

How to Use Your Inhaler

Get Ready

[figure not shown]
1. Shake the inhaler well for a few seconds before using. Remove the cap.
2. Tilt your head back slightly to straighten the airways to your lungs.
3. Hold the inhaler with your thumb on the bottom and your index or middle finger on top (see picture).
4. Breathe out fully to empty your lungs.
5. Place inhaler 1 to 2 inches in front of your open mouth.*

Inhale Slowly, Press Inhaler

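### The trial is described as double blind, but the arms get dissimilar devices and only the active leaflet prints the brand, so the blind rests on concealment and non-recognition, not on matched treatments

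*Combined protocol and SAP*

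**What the plan says.** Section 3.0 describes a "randomized, double blind, placebo-controlled, feasibility study of mometasone furoate". Section 5.3.4.1 says whom this covers: "The enrollment procedure is designed to maintain blinding of the participant, the PI and the senior RC". A second coordinator, RC2, is unblinded by design.

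Section 4.3 gives each participant "one 60-dose mometasone twisthaler or one placebo metered dose inhaler MDI", according to arm. The packets carry different leaflets. Module A is described there as "a document that has training and usage instructions for the mometasone twisthaler"; Module B serves the placebo inhaler. In Supplement 3, Module A has a heading "HOW TO USE ASMANEX TWISTHALER OR GIVE TO YOUR CHILD" and describes a dry-powder device with a twist-off cap and a dose counter. Module B gives steps for a pressurised inhaler, beginning "Shake the inhaler well for a few seconds before using. Remove the cap", and names no device brand.

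Section 8.5 gives the week-8 adherence check to RC2 because doing it means seeing the inhaler, which the section regards as unblinding. Section 5.3.4.7 has participants put the inhaler away so that other staff do not see it.

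**The concern.** In a placebo-controlled trial, double blind normally means that the treatments cannot be told apart by those receiving or assessing them. Here they can be told apart by shape, by handling and, in one arm, by a printed brand name. With 2:1 allocation of 45 participants, 45 × 2/3 = 30 people receive the branded leaflet and handle the branded device for 16 weeks.

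The clinical outcomes compared by arm in section 14.7 are largely self-reported: pain diary scores and their summaries, and change in ASCQ-Me. Section 14.3 adds self-reported respiratory symptoms. Reports of this kind respond to expectation. Section 2.3 accepts that risk, since it keeps the study acronym out of participant materials to avoid suggestion. Section 14.3 presents these measures as candidate outcomes for a definitive trial, so a distortion could carry over into its design. A reader told only that the pilot was double blind would not know to allow for it.

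**Working it through.** The point rests on comparing sections; the plan states no figure for it that could be reproduced.

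**Who is meant to be blinded, and what protects each**

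| Role | Protection in the documents | What the protection depends on |
|---|---|---|
| Participant | Sees one device only; both modules say the inhaler may hold placebo or mometasone; Module B's title area also carries the drug's generic name | Not recognising the Twisthaler or its brand, and not learning that the other arm has a different device |
| PI and SRC | Sealed, letter-coded packets and a master list withheld from them (4.3); SRC out of the room while RC2 randomizes and trains (5.3.4.7); RC2 handles refills, adherence checks, collection and replacement (8.4, 8.5, 10.3, 12.0); device put away (5.3.4.7, 8.4) | These procedures holding at every contact, and participants not showing or describing the device |
| RC2 | None; unblinded by design (5.3.4.1) | Not applicable, but section 11.4 lets RC2 administer CRF 7 at week 20 |

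**Whether the treatments are matched**

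1. Section 4.3: different devices and different leaflets.
2. Supplement 3: different technique. Module A has a twist cap and a fast, deep breath; Module B has a shaken canister held away from the mouth, pressed during a slow breath.
3. Supplement 3: the brand is printed in Module A's instructions for using and replacing the device; Module B has no device brand.
4. No section describes a matched placebo, a double dummy or a masked device.
5. Section 8.5 accepts that sight of the inhaler unblinds. Section 4.3 also states which device belongs to which arm, so anyone who knows the manual and sees one inhaler knows that participant's allocation.

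**Which comparisons are exposed**

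- Self-reported outcomes compared by arm (14.3, 14.7): exposed.
- eNO, sVCAM and the other laboratory measures (14.4, 14.10): less exposed, being instrument or assay readings.
- Feasibility (14.2, 14.6): compared by recruitment site, not arm, so little affected, although adherence and diary completion could still differ between arms.

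**Illustration of the stakes (the size of the shift is assumed)**

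Inputs: section 14.8 gives power 0.74, 0.77 and 0.80 for a 1-point difference in mean pain score at correlations 0.40, 0.30 and 0.20. Two-sided alpha of 0.05 and a normal approximation are assumed, since no alpha is stated.

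Implied standard error: SE = 1 / (1.960 + z_power).

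- Power 0.74: 1 / (1.960 + 0.643) = 0.384
- Power 0.77: 1 / (1.960 + 0.739) = 0.371
- Power 0.80: 1 / (1.960 + 0.842) = 0.357

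If knowledge of treatment shifted the between-arm difference by b with no true effect, the false-positive rate would be Φ(−1.96 − b/SE) + 1 − Φ(1.96 − b/SE). For b = 0.25 and SE = 0.384, b/SE = 0.651, which gives 0.0045 + 0.0953 = 0.100.

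| Assumed shift b (points) | SE 0.384 | SE 0.371 | SE 0.357 |
|---|---|---|---|
| 0.1 | 5.8% | 5.8% | 5.9% |
| 0.25 | 10.0% | 10.4% | 10.8% |
| 0.5 | 25.6% | 27.1% | 28.8% |

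The table shows only how sensitive the pain comparison would be. It does not say that a shift of any given size occurs.

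**The case against.** The other side has real substance. The plan takes considerable trouble over staff blinding, and hiding the inhaler is only one of several safeguards. Participants see a single device, and nothing in the supplied text tells them that the arms differ by device. Both leaflets say that the contents may be placebo or drug, and both are titled as adapted from the mometasone package insert, so the generic name reaches both arms. The brand appears in only part of Module A. Visits take place in private areas, so comparison of devices between participants is possible but undocumented. The primary outcome is feasibility, no primary clinical outcome is named, and section 14.3 already warns that the effect estimates will be imprecise.

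All of this stands, and it rules out several stronger readings that a reader might infer:

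- That the trial is effectively open label, or that every active-arm participant knows the allocation. A brand name tells a participant which product the device is; beside a statement that it may hold placebo, it does not by itself prove that the device is active.
- That the SRC is protected by nothing more than participants hiding the inhaler. The procedures listed above contradict this.
- That the plan contains no check of the blind. The supplied text shows none, but CRFs 5 and 6 are not reproduced, so their content cannot be judged.
- That a particular bias in pain score can be stated. The documents give no figure from which to derive one.

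What the objection does not answer is that the treatments are distinguishable, that section 8.5 treats sight of them as unblinding, and that section 3.0 does not disclose this. Imprecision is also a different matter from bias: a caveat about the one does not cover the other.

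**Conclusion.** The point holds in limited form. Blinding is attempted, and for the PI and SRC it is reasonably well organised. It rests on concealment procedures for those two roles and on non-recognition for participants; it is not secured by matched treatments. The consequence is confined mainly to self-reported outcomes compared by arm. Feasibility is little affected, and eNO, sVCAM and other laboratory measures are less exposed.

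The size of any bias is unknown. The illustrated false-positive rates, about 6% for a 0.1-point shift up to 26–29% for 0.5 point, depend on the assumed shift, on two-sided alpha of 0.05 and on the standard errors implied by section 14.8. They are a reason to measure the blind, not an estimate of harm. This should be corrected because the stated design property is incomplete and the correction is cheap; it does not undermine the primary aim.

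**What to change.** 1. **Leaflets and device.** Remove the brand name from Module A and use the same neutral drug wording in both modules, keeping each device's own technique steps. Mask the brand on the device without covering the dose counter or the cap label, on which Module A asks participants to write the opening date.
2. **Check of the blind.** Unless the CRFs already contain one, add a treatment-guess question for participant and SRC at weeks 8 and 16 (CRF 5 and CRF 6), and report the answers by arm. At week 16, ask it before any disclosure of allocation under section 10.4.
3. **Description.** In section 3.0, state who is blinded and by what procedures, that the devices are dissimilar, and that RC2 is unblinded and may administer CRF 7. Report between-arm patient-reported effects with that caveat.

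The cost is a leaflet edit, some masking at packaging, one CRF item and a few sentences. No new placebo device is needed. The downside is a less favourable description of the design. The schedule of changes in Supplement 1 records data collection as complete in October 2016, so for this trial item 3 is what can still be acted on; items 1 and 2 apply to any trial built on it.

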4.1 Storage of study materials

4.2 The IMPROVE research cart

A mobile research cart will be maintained by the SRC. The research cart is equipped with a laptop, FVL machine (spirometry machine) with 3L syringe, disposable mouth pieces and nose plugs; mini centrifuge with micro tubes and pipettes. The research cart will also be stocked with study medication packets (closed envelopes which contain training materials and study medication or placebo), study binders (study logs, enrollment paperwork), and the NIOX MINO exhaled nitric oxide measuring device.

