5.3.4.7 Randomization

Randomization will use an adaptive biased coin algorithm using the software program R as the user interface. After CRF 4 is complete the SRC will leave the room and the second RC (referred to as RC2 from this point forward) will enter to perform the randomization process.

RC2 will enter the room with the IMPROVE research cart and open the study laptop. RC2 will open R and load the randomization algorithm program. The program will prompt RC2 to enter a) whether or not the patient takes hydroxyurea and b) how many ED visits or hospital admissions for pain the patient has had over the preceding year c) the patients unique study identification number. The randomization algorithm will then notify RC2 which treatment arm the patient has been assigned to using a letter code (treatment arm A or B). Labeled study packets will be kept in the research cart and RC2 will hand the participant an appropriately labeled packet. At this time RC2 and the participant will open the packet together to review the study materials. The steps will be as follows:

1. Inhaler training – RC2 will train the participant in proper use of the inhaled medication including inhalation technique dosing intervals, what to do about missed doses.
2. Pain diary training – RC2 will train the participant regarding proper use of the pain diaries.
3. Contact information – RC2 will instruct the participant about how to contact study personnel in the event that the participant loses medication, has questions, suffers adverse events.

Once the training is complete, the participant will be instructed to put away their medication so that other study personnel do not see it. RC2 will leave the room.

The SRC will then enter the room and explain the schedule of financial incentives. The participant will be given a \$30 gift card and a \$11 metro card. A second follow up visit will be scheduled for 8 weeks from the current date. At this point the participant will be released and any other medical care will resume.

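### Arm-level packet codes on a cart kept by the blinded senior coordinator weaken the staff blind under 2:1 allocation

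*Combined protocol and SAP*

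**What the plan says.** - **Who is blinded.** Section 5.3.4.1: "The enrollment procedure is designed to maintain blinding of the participant, the PI and the senior RC". One coordinator, RC2, is unblinded.
- **What is on the packet.** Section 4.3 has the packets sealed and coded: "The code will indicate which treatment arm the packet corresponds to". The stated safeguard is a list: "The unblinded RC will have access to a master list that reveals the coding scheme, SRC and PI will not have access to this list".
- **How a packet is chosen.** Section 5.3.4.7 has the program report the assignment to RC2 "using a letter code (treatment arm A or B"), and then: "Labeled study packets will be kept in the research cart and RC2 will hand the participant an appropriately labeled packet".
- **Who keeps the cart.** Section 4.2: "A mobile research cart will be maintained by the SRC". The same section adds: "The research cart will also be stocked with study medication packets".
- **Allocation.** Section 3.0 plans 45 participants "with 2:1 allocation of drug to placebo".
- **Other protections.** The SRC is out of the room while RC2 randomizes and trains, and the participant puts the inhaler away before the SRC returns (5.3.4.7). RC2 handles refills (8.4), adherence checks (8.5, 10.3) and lost inhalers (12.0).
- **Disclosure during the trial.** Under sections 10.4 and 11.3, RC2 discloses the arm of any participant who wants to continue treatment. For mometasone recipients the PI then contacts the treating physician. Neither section defers this until other participants have finished.

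No section describes packet-specific numbers, several codes per arm, or stock control kept out of the SRC's sight.

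**The concern.** A code shared by everyone in an arm is only as safe as the secrecy of what it means. Two letters used in a 2:1 ratio give that meaning away gradually, because the letter that runs down faster is probably the active drug. The person best placed to notice is whoever looks after the stock, and the plan gives that job to the SRC.

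The SRC also collects outcomes. The SRC administers CRF 5 at week 8 and CRF 6 at week 16 (8.6.1, 10.5), which cover respiratory symptoms, quality of life, adverse events and side effects. The SRC also appears to perform the spirometry, since section 2.3 has the SRC's past test results reviewed for reproducibility. Section 5.3.4.5 requires the tester to urge the patient on during the manoeuvre. Interviewing and coaching are both open to influence from a suspected assignment. Because the two inhalers differ visibly (a Twisthaler and a metered dose inhaler, section 4.3), the staff blind depends wholly on concealment, and the labelling is part of that concealment.

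**Working it through.** The plan gives no figure for the strength of the blind, so there is none to reproduce. The check asks how fast packet use reveals the letter-to-arm map, and then what more is needed to reach an individual.

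**1. Inputs.** Two codes (5.3.4.7 read with 4.3), 2:1 allocation and 45 participants (3.0). Let n be the number of first packets, one per randomized participant. Week 8 refills repeat a participant's letter and are not counted.

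**2. Guessing by majority.** With independent draws, the number of mometasone packets is X ~ Bin(n, 2/3). The rule that the more-used letter is mometasone is right with probability P(X > n/2).

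- n = 9: (4032 + 5376 + 4608 + 2304 + 512) / 19683 = 16832 / 19683 = 0.855
- n = 15: 0.912
- n = 30: 0.957, or 0.969 if a tie is settled by a coin toss
- n = 45: 0.990

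**3. Strength of evidence if use runs exactly 2:1.** Each extra packet of one letter doubles the odds, since (2/3)/(1/3) = 2. The counts differ by n/3, so from even prior odds the probability of the correct map is 2^(n/3) / (1 + 2^(n/3)).

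- n = 9: 8/9 = 0.889
- n = 15: 32/33 = 0.970
- n = 45: 32768/32769, above 0.9999

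**4. Sensitivity to the algorithm.** Section 2.3 specifies an adaptive, covariate-balanced biased coin and gives no parameters. A simplified simulation ignored covariates and assumed probability 0.8 of assigning whichever arm is behind its 2:1 share. Ties count as one half in both columns.

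| n | Independent draws | Biased coin (0.8 assumed) |
|---|---|---|
| 10 | 0.855 | 0.94 |
| 15 | 0.912 | 0.985 |
| 20 | 0.935 | 0.99 |

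Under this assumed coin the independence assumption is the milder one, because balancing holds the counts closer to 2:1.

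**5. Disclosure under 10.4 or 11.3.** If each completer asks to continue with probability q (assumed; the plan gives none), the chance of at least one disclosure among m completers is 1 − (1 − q)^m.

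| q | m = 10 | m = 20 |
|---|---|---|
| 5% | 0.40 | 0.64 |
| 10% | 0.65 | 0.88 |
| 20% | 0.89 | 0.99 |

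The change log dates first enrolment to February 2014 and the end of data collection to October 2016, so follow-up is staggered and an early disclosure can fall while others are still being followed. It settles the map only for someone who also knows that participant's letter.

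**6. From the map to a person.** The SRC also needs to know which letter a given participant received. One route is to see which label is missing from the cart after an enrolment. Another may be the cart laptop: it runs the program (2.3), takes the study ID (5.3.4.7) and, being adaptive, must use past assignments. The plan does not say where that history is stored or who can open it.

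**7. What is exposed.** CRF 5, CRF 6 and week 8 spirometry (FEV₁/FVC is a secondary outcome, 14.4) are obtained after randomization. CRF 4 is finished before it (5.3.4.7).

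**The case against.** The strongest reply has four parts.

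- **Two printed codes are inferred.** Section 5.3.4.7 gives the letter as what the program tells RC2 and does not say that the letter is the packet label. A master list could serve several codes per arm. This stands as a caution, but nothing in the text describes such a scheme, and a code that denotes the arm, matched to an A or B assignment, reads most naturally as two codes.
- **The map alone unblinds nobody.** A reader might infer that 2:1 stock use reveals every participant's arm. The documents do not support that. The participant-to-letter link is partly guarded by the SRC's absence, by RC2 bringing in the cart and by the inhaler being put away, and no section has the SRC count or log labels. The probabilities above measure a guess at the map by someone who watches all packet use. They are not probabilities of unblinding.
- **One disclosure does not break the code for all.** A reader might infer this from section 10.4. That section discloses an arm, not a letter, and does not say the SRC is told. The PI, who learns of mometasone recipients, does not keep the cart and would need the letter from elsewhere.
- **Consequences are limited.** The primary outcome is feasibility, built on follow-up, participant-completed diaries and dose counters. eNO and sVCAM are a device reading and an assay. CRF 4 cannot be affected at all. This stands.

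It is also fair that section 4.3 already gives packaging and distribution to staff assisted by the unblinded coordinator, and that section 4.2 does not say who loads the cart. Even so, the SRC maintains the cart that holds the coded packets.

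**Conclusion.** The concern holds as a weakness in the staff blind. It is not a demonstration that anyone would be unblinded. With an arm-level code, two apparent letters, 2:1 allocation and a cart kept by a blinded assessor, withholding the master list protects little: the letter-to-arm map can be guessed correctly with probability about 0.86 after 9 packets, 0.91 after 15 and 0.99 after 45. These figures assume two codes, sight of all packet use and independent draws. A disclosed arm would settle the map for anyone who also knows that participant's letter. Reaching an individual still requires seeing which label left the cart, or access to the assignment history.

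The outcomes at risk are the SRC-administered CRF 5 and CRF 6 and the coached spirometry. Feasibility, eNO and sVCAM are little exposed. The change is worth making because it costs little and closes an avoidable route to bias.

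**What to change.** 1. Label each packet, including refills and replacements, with a unique number that carries no arm information.
2. Have the R program return a packet number to RC2 in place of A or B.
3. Keep the number-to-arm list and the assignment history accessible only to unblinded staff, including on the cart laptop.
4. Have RC2, not the SRC, stock and carry the packets, and reword sections 4.2, 4.3 and 5.3.4.7 to match.

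With unique numbers, a disclosure under 10.4 or 11.3 reveals that participant's arm and says nothing about anyone else's packet.

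The cost is relabelling, one change to the script and some stock-tracking work for RC2, who already helps to package and distribute the medication. No new staff are needed, and sample size, visits and treatment are unchanged.
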